12 STUDY PROCEDURES

12.1 Prestudy

An ICF must be signed and dated by the patient, the Investigator or designee and witness (if required) before any study-related procedures are performed.

12.2 Screening Visit

Screening assessments will be performed within 28 days (+ 14 days) of BMN 270 infusion while baseline assessments will take place within 7 days of BMN 270 infusion (Day 1). Should the screening visit occur within 7 days of the drug infusion, physical examination, vital signs, blood chemistry, LTs, haematology, urine tests, coagulation screen, and CRP do not need to be repeated at Baseline.

The following procedures will be performed during the Screening Period:

- Full medical history, including haemophilia A history, hepatitis B, hepatitis C, and HIV.
 - Subjects with a history of hepatitis B or hepatitis C will be asked for information about the treatments received. Any prior pharmacokinetics information obtained while the subject was receiving prophylactic or on-demand FVIII therapy prior to the study should also be collected. For subjects who have already enrolled in 270-201, this information should be collected at the next regularly scheduled study visit (or at least prior to the subject's completion of study participation).
- Complete Physical Examination
- Height and weight
- Vital Signs (systolic and diastolic blood pressure, heart rate, respiration rate, and temperature)
- Assessment of Adverse Events and Concomitant Medications
- Documentation of bleeding episodes and FVIII usage (by either subject or clinical information)
- Electrocardiogram
- Chest X-ray
- Liver Ultrasound
- Samples for hFVIII Assays
 - Baseline hFVIII activity chromogenic substrate (plasma)
 - Baseline hFVIII activity level one-stage clotting assay

270-201 Amendment 10

- hFVIII coagulation activity exploratory assay
- hFVIII inhibitor level (Bethesda assay with Nijmegen modification)
- hFVIII total antibody assay
- hFVIII antigen (ELISA)
- Blood sample for AAV5 Assays
 - o AAV5 antibody titer
 - o AAV5 transduction inhibition assay
- Screen for hepatitis B, hepatitis C, and HIV if required (subjects with documented negative results 30 days prior to informed consent being obtained do not need to be retested)
- Blood chemistry, haematology, coagulation screen, and CRP (refer to Table 9.7.9.2.1)
- Urine Tests (refer to Table 9.7.9.2.1)
- Liver Tests (refer to Table 9.7.9.3.1)
- Von Willebrand Factor Antigen (VWF:Ag)
- Blood samples for Biomarker testing (including HLA genotyping, FVIII genotyping status, TNFα and IL10a single nucleotide polymorphisms)

12.2.1 "Smart Rescreening" Visit

Subjects who undergo smart rescreening must complete the rescreening assessments and receive the infusion within 90 days of signing the original consent. Subjects who do not complete dosing within 90 days will be required to re-consent and undergo all screening procedures. Subjects may not undergo smart rescreening more than once.

If a patient has to be screened again because the original assessments have fallen out of the 28 + 14 day period allowed for Screening (refer to Section 12.2), then only the following assessments need to be performed (rather than the full list indicated in Section 12.2) for the patient to be successfully re-screened for the study:

- Vital signs
- Assessment of Adverse Events and Concomitant Medications
- Documentation of bleeding episodes and FVIII usage (by either subject or clinical information)
- hFVIII Assays (only the hFVIII inhibitor level (Bethesda assay with Nijmegen modification)
- Blood sample for AAV5 Assays

- o AAV5 antibody titer
- $\circ \quad AAV5 \ transduction \ inhibition \ assay$
- Blood chemistry, haematology, coagulation screen, and CRP (refer to Table 9.7.9.2.1)
- Urine Tests (refer to Table 9.7.9.2.1)
- Liver Tests (refer to Table 9.7.9.3.1)

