Haemo-QoL-A Quality of Life (QoL) assessment			X	
BMN 270 Infusion				Х

Proprietary and Confidential

BOMARIN

270-201 Amendment 10

- ^a Complete physical examination should be done at Screening. Brief physical examination may be done at Baseline and at the BMN 270 Infusion Visit. Height will be recorded at Screening only. Weight will be recorded at Screening and then every 6 months thereafter.
- ^b Includes baseline hFVIII activity (chromogenic substrate assay and one-stage clotting assay), hFVIII coagulation activity exploratory assay, hFVIII inhibitor level (Bethesda assay with Nijmegen modification), hFVIII total antibody titer, and hFVIII antigen (ELISA).
- ^c Screening (done during Screening) and testing (at Infusion Visit) of AAV5 pre-existing immunity may include plasma samples for 3 assays (in vivo transduction inhibition, in vitro transduction inhibition and AAV5 total antibody assays). Sample collection on the day of the infusion visit must be performed before the BMN 270 infusion is given.
- ^d Patients with documented negative results within the last 30 days do not need to be retested.
- ^e Refer to Table 9.7.9.2.1 for laboratory assessments to be included, and to Table 9.7.9.3.1 for liver tests.
- ^f Includes HLA genotyping, FVIII genotyping, TNFα and IL10a single nucleotide polymorphisms.
- ^g Blood samples will be collected to evaluate biochemical, molecular, cellular, and genetic/genomic aspects relevant to hemophilia A, coagulation, and/or AAV gene transfer, and to develop assays used for these evaluations. Subjects may choose to opt out of the exploratory genetic/genomic research being done to study or try to discover genes that are not yet known to be associated with hemophilia A. While exploratory samples will be collected at the time points indicated above, testing of these samples (including those for Direct Thrombin Activity test and any other exploratory assessments) will be performed only as deemed necessary by the Sponsor.
- ^h Should the screening visit occur within 7 days of the drug infusion, physical examination, blood chemistry, LTs, haematology, urine tests, coagulation screen, and CRP do not need to be repeated at Baseline.

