- ⁱ Smart rescreening should only be performed if a patient has been determined to be eligible for the study and is unable to complete the Baseline assessments and Infusion prior to the closing of the original Screening window. Subjects who undergo smart rescreening must complete the rescreening assessments and receive the infusion within 90 days of signing the original consent. Subjects who do not complete dosing within 90 days will be required to re-consent and undergo all screening procedures. Subjects may not undergo smart rescreening more than once.
- ^j Only the hFVIII inhibitor level (Bethesda assay with Nijmegen modification) assay must be done at smart rescreening.
- ^k Assessments on the day of infusion must be performed prior to the infusion. On the day of the BMN 270 Infusion, vital signs will be monitored prior to the infusion, during the infusion every 15 minutes (± 5 minutes), following the infusion hourly (± 5 minutes) for 6 hours and then every 2 hours (± 15 minutes) for 6 hours and then at 4 hour intervals (± 15 minutes).

270-201 Amendment 10

Table 9.1.2: Schedule of Events – Post-Infusion Follow-Up (Week 1-16)

					F	'ollow-	Up Af	ter BN	/IN 27	0 Adm	inistra	tion –	Week	s*				
	,	Week	1															
Assessment	D2	D4	D8	2	3	4	5	6	7	8	9	10	11	12	13	14	15	16
Physical examination ^a			X	X	X	X	X	X	X	X	X	X	X	X	X	X	Х	X
Assessment of Adverse Events and Concomitant Medications (including review of subject diary for bleeding and FVIII use)			X	X	X	X	X	X	Х	X	Х	Х	X	X	X	X	Х	X
Vital Signs			X	X	X	Х	X	X	Х	X	X	X	X	Х	X	X	Х	X
Blood chemistry, haematology, coagulation screen, and CRP ^b				X		X		X		X		Х		X				X
Urine Tests ^b						Х				X				Х				X
Liver Tests (local) ^b		X	X	X	X	Х	X	X	X	X	X	X	X	Х	X	X	X	X
FVIII assays (local) ^c		X	X	Х	X	Х	X	X	Х	X	X	X	X	Х	X	X	Х	X
Liver Tests (central) ^b		X	X	Х	X	Х	Х	X	Х	X	X	X	X	Х	X	X	Х	X
FVIII assays (central) ^d		X	X	X	X	X	X	X	X	X	X	X	X	X	X	X	Х	X
FVIII antibody titer						Х				X				X				X
PCR of vector DNA in blood, saliva, urine, semen, and stools ^e	X	X	X			X		X		X		X		X		X		X
Exploratory biomarker assessments ^f						Х				X				Х				X
Haemo-QoL-A QoL assessment			X	X	X	Х												X
AAV5 antibody titer										X								X
Testing for reactivation of hepatitis B and hepatitis C																		Xg
PBMC collection			X	Х	X	Х	Х	X	Х	X	Х	Х	X	Х	X	X	Х	X
Von Willebrand Factor Antigen (VWF:Ag)						Х				X				Х				X
Direct Thrombin test			Х												Х			

* Visit windows are \pm 48 hours (and include the Day 4 visit)

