9.3.1 Inclusion Criteria

Individuals eligible to participate in this study must meet all of the following criteria:

- 1. Males that are 18 years or older with established severe Haemophilia A as evidenced by their medical history. Patients will be considered as severe if their base FVIII level is 1 IU/dL or less
- 2. Treated/exposed to FVIII concentrates or cryoprecipitate for a minimum of 150 exposure days (EDs)
- 3. Greater or equal to 12 bleeding episodes only if on on-demand therapy over the previous 12 months. Does not apply to patients on prophylaxis
- 4. Able to sign informed consent and comply with requirements of the trial
- 5. No history of inhibitor, and results from a modified Nijmegen Bethesda assay of less than 0.6 Bethesda Units (BU) 2 consecutive occasions at least one week apart within the past 12 months
- 6. Sexually active patients must be willing to use an acceptable method of contraception such as double barrier, including hormonal contraception for at least 6 months post-treatment. After 6 months, subjects may stop contraception use only if they have had 3 consecutive semen samples below the limit of detection of the test.

BOMARIN

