9.4.8.1 Concomitant Haemophilia Treatments

Subjects on "episodic" therapy for FVIII will continue their treatment at will. Subjects on prophylactic FVIII therapy will discontinue their treatment starting the day of infusion and switch to an "episodic" schedule. FVIII can always be taken as needed by the subject, who will carefully record his treatment and bleeding episodes in his diary. In addition, information on FVIII usage by medical history will be collected (if available) from subjects for the 6 month period immediately preceding study enrollment.

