9.7.2 Primary Efficacy Variables

The primary efficacy measure will be the plasma FVIII activity monitored on a regular basis after BMN 270 dose. The efficacy goal of the protocol is to ascertain the dose range of BMN 270 required to convert severe HA patients to expression of FVIII at 5 IU/dL or above, (ie, a mild severity). This is associated in natural history studies with clinically superior long term outcomes (Den Ujil 2011).

The following assays (assessed by the central laboratory) will be used to measure the primary efficacy variable:

- FVIII activity (chromogenic substrate assay)
- FVIII activity by one-stage clotting assay

If a subject has used FVIII within 72 hours of a measurement day, all efforts should be made to obtain FVIII activity measurements when a 72-hour interval without FVIII use is achieved. The 72-hour wash-out period is only intended for subjects who have achieved FVIII ≥ 5 IU/dL at 16 weeks after BMN 270 infusion and who have not resumed standard of care FVIII replacement therapy.

The FVIII activity level in both assays and the number of subjects with FVIII activity ≥ 5 IU/dL in at least one of the two assays will be summarized.

FVIII activity assays will also be performed at the local laboratory at the time points indicated in Table 9.1.2, Table 9.1.3, Table 9.1.4, and Table 9.1.5 but will be used in conjunction with local lab LT assessments to monitor subject safety and need for initiation of reactive corticosteroid dosing; local laboratory FVIII activity assessments will not be used to assess efficacy or to measure the primary efficacy outcome of the study.

Subjects who do not respond to BMN 270 treatment (ie, treatment failure, manifesting as failure to achieve FVIII activity ≥ 5 IU/dL by Week 52 and inability to maintain independence from prophylactic FVIII replacement therapy due to joint bleeding episodes, in the judgment of the Investigator) may, at the Investigator's discretion and after discussion with the Medical Monitor, follow an abbreviated visit schedule after Week 52, as applicable and at the discretion of the Investigator.

Timing of assessment by these assays is provided in Table 9.1.2, Table 9.1.3, Table 9.1.4, and Table 9.1.5. Details on performing the assays are included in the Laboratory Manual.

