9.7.5 Pharmacodynamics

The hFVIII antigen and activity level will be measured by an ELISA (antigen) and by one-stage clotting and/or chromogenic substrate assay (activity). Individual antigen and activity plasma plots will be prepared to assess changes over 16 weeks. FVIII activity measurements will be used to determine PD parameters.

If supported by FVIII activity data, non-compartmental analysis and observation will be used to estimate individual values of C_b (baseline concentration), C_{ss} (steady state concentration), T_{ss} (time to steady state), C(t) and AUC(0-t) where t is 16 weeks. Other parameters that may be used to describe individual FVIII protein and activity plasma profiles are C_{max} (maximum concentration) and C_{avg} (average concentration, AUC(0-t)/t). The PD parameters and dose will be used to assess clinical pharmacology.

Sample collection times are indicated in Table 9.1.2, Table 9.1.3, Table 9.1.4, and Table 9.1.5.

BOMARIN

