14.2 Primary and Secondary Efficacy Analysis

The subjects will be followed in a longitudinal manner and all the relevant information will be collected. The analysis of the data will be descriptive in nature. Descriptive statistics include the number of subjects, mean, median, standard deviation, minimum, and maximum for continuous variables and count and percent for categorical variables. Efficacy variables will be summarized by dose cohort at each time point. Relationship between dose and efficacy results will be examined.

Data collected in a longitudinal manner may be analyzed using longitudinal methods such as mixed effect model which takes into account the correlation among the observation taken at various time points within a participant. Efficacy is a secondary endpoint, defined as biologically active hFVIII at ≥ 5 IU/dL by chromogenic substrate assay and/or one-stage clotting assay as measured by the central laboratory at 16 weeks following study treatment. We can only assess the true steady state of hFVIII protein produced from BMN 270 after a minimum of 72 hours has elapsed since the last infusion of FVIII protein concentrates.

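### The only pre-infusion FVIII activity sample has no condition on time since the last FVIII dose, so C_b can partly reflect exogenous FVIII in recently treated subjects

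*Protocol*

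**What the plan says.** Section 12.2 lists both baseline activity assays at Screening, the first as "Baseline hFVIII activity chromogenic substrate (plasma". Footnote b of Table 9.1.1 uses the same label: "Includes baseline hFVIII activity (chromogenic substrate assay and one-stage clotting assay". Sections 12.3 (Baseline) and 12.4 (Day 1) contain no FVIII activity assay, and a footnote on rescreening says "Only the hFVIII inhibitor level (Bethesda assay with Nijmegen modification) assay must be done at smart rescreening". The Screening draw is thus the only pre-infusion activity value.

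On treatment at that time, Section 9.4.8.1 says "Subjects on prophylactic FVIII therapy will discontinue their treatment starting the day of infusion". The washout rule in Section 9.7.2 does not reach back to Screening, because it covers only Week 16 responders (5 IU/dL or more) who remain off standard replacement: "The 72-hour wash-out period is only intended for subjects who have achieved FVIII". Section 14.2 states the principle behind the rule, with the clock running from the most recent concentrate: "We can only assess the true steady state of hFVIII protein produced from BMN 270 after a minimum of 72 hours has elapsed".

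On use of the value, Sections 9.7.5 and 14.5 plan, if the activity data support it, to estimate "individual values of C_b (baseline concentration" among other PD parameters, and 14.5 summarises them descriptively. The entry criterion in Section 9.3.1 reads "Patients will be considered as severe if their base FVIII level is 1 IU/dL or less".

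**The concern.** The protocol accepts that injected FVIII obscures the subject's own level for about three days. It guards the post-infusion readings against this but not the single pre-infusion one. The sentence in Section 14.2 concerns FVIII produced from the vector, but the reasoning is the same for native residual FVIII, because the assay reads whatever FVIII is circulating.

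At stake is the meaning of C_b, and of any descriptive comparison of later activity with baseline. An inflated baseline understates the rise after treatment. The error would differ between subjects according to product, dosing frequency and time of draw, and between those on prophylaxis and those treated episodically.

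**Working it through.** The plan gives no figure for this point, so there is none to reproduce.

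**Inputs from the protocol**
- Half-life h: about 8–12 h (Section 7) and 12–18 h (Section 7.3); 8, 12 and 18 h are used here.
- Prophylaxis: 2–3 times a week (Synopsis) or 2–4 times (Section 7.3). Two a week gives an interval T = 168/2 = 84 h; three gives 168/3 = 56 h.
- Base level: at most 1 IU/dL (Section 9.3.1).

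**Assumption.** The rise R per dose is not in the protocol. It is taken as 50 IU/dL, with 30 to 100 as the range.

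**Formulas** (first-order decay, draw at a random time in the interval)
- Average after one dose: R × (1 − 0.5^(T/h)) / (ln 2 × T/h)
- Average with carry-over from regular dosing: R / (ln 2 × T/h)
- Trough with carry-over: R × 0.5^(T/h) / (1 − 0.5^(T/h))

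Lowest case, T = 84 and h = 8: 50 × (1 − 0.0007) / (0.693 × 10.5) = 6.9. Highest, T = 56 and h = 18: 50 × (1 − 0.1157) / (0.693 × 3.11) = 20.5.

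| T (h) | h (h) | Average, one dose | Average, carry-over | Trough |
|---|---|---|---|---|
| 84 | 8 | 6.9 | 6.9 | 0.03 |
| 84 | 12 | 10.2 | 10.3 | 0.39 |
| 84 | 18 | 14.8 | 15.5 | 2.05 |
| 56 | 8 | 10.2 | 10.3 | 0.39 |
| 56 | 12 | 14.8 | 15.5 | 2.05 |
| 56 | 18 | 20.5 | 23.2 | 6.54 |

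All values are exogenous IU/dL at R = 50 and are proportional to R. With R from 30 to 100, the carry-over averages run from 4.1 (6.9 × 0.6) to 46.4 (23.2 × 2). At four doses a week (T = 42 h) and R = 50, they are 13.7 to 30.9.

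**Effect of a 72-hour condition.** The share of a dose remaining is 0.5^(72/h): 0.2% at 8 h, 1.6% at 12 h and 6.3% at 18 h. Of a 50 IU/dL rise, that leaves 0.1, 0.8 and 3.1 IU/dL. The condition removes most of the contamination, but not all of it for the longest half-life.

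**The case against.** The strongest reply is that nothing important rests on this value. The Week 16 criterion is an absolute level of at least 5 IU/dL, escalation uses absolute Week 3 levels, and severity is established from medical history. C_b is conditional and descriptive. Its source sample is not named in Sections 9.7.5 or 14.5, and its derivation is a matter the SAP may settle. All of this stands and limits the weight of the point. It does not remove it: the protocol itself labels the Screening draw as baseline and offers no alternative sample. A SAP can choose another source but cannot repair the draw.

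Three stronger readings are tempting, and the documents do not support them.
- *That the efficacy result or dose decisions are biased.* They are not, because both use absolute thresholds.
- *That a planned change-from-baseline FVIII analysis is wrong.* Sections 9.7.2, 9.7.5, 14.2 and 14.5 define none, and Section 9.2 limits pre-treatment comparison to liver function, bleeds and replacement use. Only a general sentence in the Synopsis, under reference therapy, mentions comparing FVIII activity with baseline. It is broken in the copy of Amendment 10 at hand and legible in the bundled synopses of Amendments 8 and 9.
- *That every prophylaxis subject's baseline is mainly injected FVIII.* A trough draw can be below 1 IU/dL, as the table shows. On-demand subjects without recent FVIII give a valid value.

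It is also fair to say that FVIII usage is documented at Screening, so the sample can be qualified afterwards. The protocol does not link the two.

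**Conclusion.** The point holds, with limited reach. The one baseline activity sample is not subject to the 72-hour condition that the protocol itself treats as necessary for reading non-injected FVIII. In subjects with recent FVIII use, C_b and any descriptive comparison with baseline can therefore reflect exogenous FVIII. The likely size is an average of roughly 7 to 20 IU/dL against a base level of at most 1 IU/dL, and near or below 1 IU/dL at some troughs.

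This rests on the assumed 50 IU/dL rise, first-order decay, half-lives of 8 to 18 h, two to three doses a week and a draw at a random time in the interval. The number of subjects on prophylaxis is not stated, so the effect on cohort summaries cannot be sized. Correcting this is worthwhile because it is almost free; the main conclusions do not depend on it.

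**What to change.** Change Sections 9.7.5 and 14.5 only; no treatment or visit changes.
1. Derive C_b only from Screening samples taken at least 72 hours after the last FVIII dose, the protocol's own condition. Note that about 6% of a dose remains at an 18 h half-life. A sample whose interval cannot be established counts as not meeting the condition.
2. Otherwise use the subject's documented historical residual level where one is on file. The entry criterion relies on medical history and does not expressly require a numeric value, so availability must be checked. Handle levels reported as below 1 IU/dL by one stated convention, since a bound is not a value.
3. If neither source exists, report C_b as not estimable.
4. State that this is a rule on the source of the value and not imputation, so that it is consistent with Section 14.1.2, which rules out imputing missing data.
5. List every Screening activity value with hours since last FVIII, taken from the usage already documented at that visit.

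The cost is a few sentences and one listing. The Amendment 9 summary says recruitment is complete, so only a repair in the analysis can reach the enrolled subjects.

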12.3 Baseline Visit

Baseline values will be recorded from 1 to 7 days prior to the treatment visit. The following procedures will be performed during the Baseline Period:

- Physical examination
- Assessment of Adverse Events and Concomitant Medications
- Documentation of bleeding episodes and FVIII usage (by either subject or clinical information)
- Distribution of subject diaries and training in diary completion
- Blood chemistry, haematology, coagulation screen, and CRP (refer to Table 9.7.9.2.1)
- Urine Tests (refer to Table 9.7.9.2.1)
- Liver Tests (refer to Table 9.7.9.3.1)
- PBMC collection for CTL baseline
- Direct Thrombin test
- PCR of vector DNA in blood, saliva, urine, semen, and stools
- Exploratory biomarker assessments
- Haemo-QoL-A QoL assessment

12.4 Treatment Visit/BMN 270 Infusion Visit (Day 1)

There will be one treatment visit for each subject. Subjects will remain in the clinic for 24 hours for the BMN 270 Infusion Visit. The following procedures will be performed during the BMN 270 Infusion Visit:

- Physical examination
- Assessment of Adverse Events and Concomitant Medications
- Blood sample for AAV5 Assays (must be performed before the BMN 270 infusion)
 - o AAV5 antibody titer
 - AAV5 transduction inhibition assay

- BMN 270 Infusion
- Vital Signs
 - Vital signs will be recorded prior to BMN 270 infusion and then every 15 minutes (± 5 minutes) during BMN 270 infusion. Following infusion, vital signs will be monitored every 1 hour (± 5 minutes) for the first 6 hours, every 2 hours (± 15 minutes) for the next 6 hours, and then at 4 hour (± 15 minutes) intervals for the remainder of the subject's stay in the clinic.

